In Experiment 1, participants will be required to learn an upper limb precision aiming task while receiving postural support (i.e., balance facilitation) or no postural support. Baseline performance will be measured prior to a practice period. For this pre-test, participants will stand on the force platform for 30 s trials. Within the VR environment, participants will see an anteriorly placed circular target and will be instructed to maintain the position of a virtual laser pointer in the target via a handheld device in the dominant hand (or both the non-paretic and paretic hands for participants with stroke) with the upper limb held at the side. The target will change color to communicate task accuracy to participants: When the virtual laser is correctly positioned within the target, the target will be blue, but misaiming will turn the target red, indicating the need to correct the laser position. Participants will only visualize the laser and target in VR; there will not be a virtual representation of the upper limb. Participants with stroke will complete two 30 s pre-test trials with each hand (paretic and non-paretic). Postural sway and projection of the laser will be measured and recorded.

Transfer Task

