As therapists expect that training in a set of tasks might benefit performance of other similar but untrained tasks (i.e., transfer), a task to assess transfer will also be implemented. This task will be completed both prior to the practice period (to obtain a baseline level of performance for comparison after practice) and after the practice period. In the transfer task, participants will attempt to use their dominant hand (or both non-paretic hand and paretic hand for participants with stroke) second digit to produce a specified level of light touch force (0.5-1 N to prevent physical stabilization) on the force transducer. Like the laser pointer task, this task requires integration of postural control with precision manual performance (e.g., Riley et al., 1999b). Participants will receive visual feedback regarding their level of light touch force production on a visual display. A vertical bar will appear on the screen. The bar will increase in vertical size with increased force production and decrease in size with less force production. The bar will change color to reflect the level of force production. When the bar is blue, the desired level of force production has been achieved. When the bar is red, the participant needs to alter the level of force production. A horizontal line will also indicate target force production. Participants will complete two 30 s trials of the transfer task. Participants with stroke will complete the transfer trials with each limb.

Practice

Following the pre-test and baseline transfer task, participants will engage in 10, 1 min practice blocks in which they are to practice the laser task with the target positioned

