laterally. This lateral placement of the target during the practice period (as opposed to the anterior position of the pre-test) will prevent one group of participants from practicing under the exact conditions of the pre-test, which could bias the results. This will also allow for an assessment of differences in sway variability that may facilitate performance at post-test, thus providing insights about generalizability. The control group will receive no physical support to maintain balance. The experimental group will receive physical support (whether physical support is warranted or not) to minimize postural sway fluctuations. Participants with stroke will use the paretic hand. Participants will be outfitted with a gait belt, and physical support will be provided through the use of the gait belt and other traditional physical therapy guarding techniques (O'Sullivan et al., 2019). Thus, participants in this group will not be required to coordinate posture and task performance because postural stabilization will be provided externally through physical support. Postural sway and virtual laser position will be synchronously recorded during the practice period. Participants will rest for a self-selected period between each trial.

Immediate Post-Test and Retention

Participants will complete a post-test following the same procedure as the pre-test (i.e., target task). The post-test will also involve the previously described transfer task. Participants will complete two 30 s trials of each task (target/force production). Participants with stroke will complete the trials with each limb. Task and condition will be randomized. No physical support will be provided in the post-test.

Design

To evaluate the learning effect in participants with stroke, the two groups (experimental, control), two hands (paretic, non-paretic), and two test conditions (pre-test, immediate post-test) will result in a $2 \times 2 \times 2$ mixed design for Experiment 1. Participants with stroke will complete 2 trials of each test condition per limb for a total of 8 test trials per participant. To evaluate the role of therapist support during practice, each participant will complete 10 practice trials. Participants will complete 4 trials (2 trials per limb) of the transfer task before and after practice for a total of 8 trials.

Proposed Data Analysis

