Due to the wide use of COP path length and standard deviation (SD) of COP in the literature, these metrics will also be measured to further quantify changes in postural sway. These metrics are also important for assessing the distribution of sway in each plane as a function of task demand. COP path length refers to the amount of displacement of the location of the (resultant) vertical ground reaction force vector. Increased COP path length is often interpreted as reduced stability. SD of the COP is the typical method used to quantify the variability in COP trajectories. Higher values for SD of the COP indicate increased variability. COP path length is a bi-planar measure whereas SD of the COP will be calculated separately for each plane.

Supra-Postural Task Performance

Root mean square (RMS) deviation of the observed supra-postural task performance from the expected values will be used to determine the accuracy of supra-postural task performance. For Experiments 1 and 2, this will be defined as the deviation of the laser position from the target. For the transfer task, this will be defined as the deviation from the target range of light touch force production.

Statistical Analysis

To characterize learning of the practiced supra-postural laser/target task and the associated postural sway patterns, trials (error score and postural sway metrics) for both experiments will be submitted to mixed-effects models. Group (experimental, control), test condition (pre-test, immediate post-test), limb (paretic, non-paretic), and their interactions will be entered as fixed effects, and participant will be entered as a random effect. To assess performance (error score and postural sway metrics) during the practice period, trial number (1-10), group (experimental, control), and their interaction will be

entered as fixed effects and participant will be a random effect. For the transfer task (error score and postural sway metrics), group (experimental, control), test condition (pre-test, immediate post-test), limb (paretic, non-paretic), and their interactions will be entered as fixed effects, and participant will be entered as a random effect. A backward stepwise approach will be used for model building. Simple effects and pairwise comparisons will be used to follow up on significant interactions.

Relevant References

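### The practice-period model does not use the paretic-hand pre-test already collected, so its group main effect is less precise than it could be; the estimate itself is valid.

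*Combined protocol and SAP*

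**What the plan says.** The Design section gives the practice comparison its own aim: "To evaluate the role of therapist support during practice, each participant will complete 10 practice trials". The Statistical Analysis section sets out the model: "To assess performance (error score and postural sway metrics) during the practice period, trial number (1-10), group (experimental, control", plus the interaction of the two, "entered as fixed effects and participant will be a random effect". No pre-test or other baseline value is among the terms. Model building is backward stepwise, which can remove terms from this list but cannot bring in one that was never entered.

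The baseline exists. Under Pre-Test: "Participants with stroke will complete two 30 s pre-test trials with each hand (paretic and non-paretic". Sway and laser position are recorded in those trials, before practice and without support. Under Practice: "Participants with stroke will use the paretic hand", and the same two signals are recorded again.

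Pre-test and practice conditions are not identical. Practice consists of "10, 1 min practice blocks", and the plan points out the "lateral placement of the target during the practice period (as opposed to the anterior position of the pre-test".

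**The concern.** The participant random effect handles the repeated trials, but it does not adjust the group contrast for how well each person performed beforehand. Ten trials per person do little for the group contrast, because most of the variance of a 10-trial mean lies between people. Eligibility allows Modified Rankin scores of 0 to 3 and, until narrowed, ages 21 to 85, so the spread between people may be wide. A pre-test value of the same metric on the same hand is the obvious covariate for that component. At stake is the precision of the one comparison that looks directly at performance while support is being given.

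**Working it through.** **Inputs from the documents.** 10 participants per group, randomly assigned (Participants); 10 practice trials (Design); two paretic-hand pre-test trials (Pre-Test).

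**Assumptions, because the documents give no figure.** Two-sided alpha 0.05; 1-SD group effect, where SD is that of a participant's mean over the 10 practice trials; complete data; r is the correlation of the pre-test mean with the practice mean, shown as a range. The plan contains no sample-size calculation to reproduce.

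**1. Reduction to participant means.** With complete, balanced trials, a participant random intercept and centred trial number, the model's group effect is the difference in participant means. On simulated data the two analyses gave the same standard error (0.5403), and adding the covariate left the trial-by-group standard error unchanged (0.0493). If the correlation between trials within a person is 0.5 (assumption), the between-person share of the variance of a 10-trial mean is 0.5/(0.5 + 0.5/10) = 0.91.

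**2. Unadjusted, as planned.** SE = sqrt(2/10) = 0.447 SD. Half-width = t(0.975, 18 df) × SE = 2.101 × 0.447 = 0.94 SD. Power from the noncentral t distribution, noncentrality 1/0.447 = 2.236: 56%.

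**3. Adjusted, common slope.** The variance relative to unadjusted is (1 − r²) × (1 + 1/(20 − 4)) = (1 − r²) × 1.0625, with 17 df and t = 2.110.

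| r | Variance ratio | 95% half-width (SD) | Power, 1-SD effect |
|---|---|---|---|
| unadjusted | 1 | 0.94 | 56% |
| 0.2 | 1.02 | 0.95 | 55% |
| 0.4 | 0.89 | 0.89 | 61% |
| 0.5 | 0.80 | 0.84 | 66% |
| 0.7 | 0.54 | 0.69 | 82% |

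Break-even on variance: r = sqrt(1 − 1/1.0625) = 0.24.

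**4. What r might be.** With a trial correlation of 0.5 in both conditions, a 2-trial mean has variance 0.5 + 0.5/2 = 0.75 and a 10-trial mean 0.5 + 0.5/10 = 0.55. So r = 0.5/sqrt(0.75 × 0.55) = 0.78 times the correlation of true levels between the two conditions. If that correlation is 0.8, 0.6 or 0.4 (assumptions), r is 0.62, 0.47 or 0.31, and power with a common slope is 74%, 64% or 58%.

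**5. If support weakens the relation.** With unit variances in each arm, the common-slope model behaves as if r were the average of the two arms' slopes. Halving the slope in the supported arm gives 0.75r:

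- r = 0.62: 0.465, variance ratio 0.83, power 64%
- r = 0.47: 0.353, variance ratio 0.93, power 59%
- r = 0.31: 0.233, variance ratio 1.01, power 56%

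If support removes the slope entirely, control/supported slopes of 0.7/0 average 0.35, with variance ratio 0.93 and power 59%. Slopes of 0.5/0 average 0.25, with variance ratio 1.00 and no gain. Simulation confirmed these powers, with type I error about 5%.

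**The case against.** The strongest reply is that nothing here is wrong: random assignment makes the planned contrast unbiased, and the model is a legitimate choice. That stands. A reader might infer from the missing baseline that the practice comparison is biased or that its false-positive rate is inflated. The documents do not support either inference.

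A reader might also treat chance imbalance as a second harm. Two groups of 10 differ by more than 0.5 SD at pre-test with probability 2 × (1 − Φ(0.5/0.447)) = 26%. That uncertainty is already inside the ±0.94 SD interval, so it must not be counted again.

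The gain itself is uncertain. Target position and trial length differ between pre-test and practice. A covariate needs only correlation, so this does not rule it out, but it does make a high r unsafe to assume. Support is given "to minimize postural sway fluctuations", so unsupported sway may predict supported sway poorly. Counting two planes, the plan defines 11 sway metrics (five computed per plane, plus path length) and one error score, so most outcomes may gain little or nothing. The error score is not exempt either: the Practice section expects supported participants to be relieved of coordinating posture with the task, which could weaken its relation to pre-test error as well. All of this stands, and it makes the benefit conditional.

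Finally, a reader might extend the point to the learning and transfer models. Those already use the pre-test as a level of test condition. Choosing between that change contrast and a baseline-adjusted one is a modest efficiency preference, and per-limb adjusted contrasts would add many comparisons. The point is confined to the practice model.

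**Conclusion.** The point holds as a matter of precision. The practice model leaves out a relevant pre-support measurement that every participant will have, and its group main effect is therefore an unadjusted 10-versus-10 comparison. Under the assumptions stated, adjustment changes power for a 1-SD effect from 56% to between 55% and 82% as r runs from 0.2 to 0.7 with a common slope. With the supported-arm slope halved, it reaches about 64%, 59% or 56% at r = 0.62, 0.47 or 0.31. A worthwhile gain is plausible mainly for the error score and only at moderate or higher r; for sway it may be small or nil. Since neither r nor the effect size is in the documents, no single figure can be promised. This is a low-cost improvement, and the plan is valid without it.

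**What to change.** Add to the practice model each participant's mean paretic-hand pre-test value of the same metric, centred, as a prespecified covariate that backward elimination may not remove. Centre trial number so that the group term is the average difference over the 10 trials. With trials coded 1 to 10 and the interaction present, the group coefficient refers to trial 0, which does not exist. Keep one common slope; for sway metrics, a group-by-pre-test slope can be reported as a sensitivity analysis but should not be used to choose the model. State in the SAP that the gain depends on an unknown correlation and is expected mainly for the error score. Settle this before the data are seen, because adding baseline after noticing an imbalance would be a data-driven choice.

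The cost is a sentence or two in the SAP and one degree of freedom, with no new data. The downside is a slight loss of precision if r is below about 0.24: at r = 0 the variance rises by about 6% and power for a 1-SD effect falls from 56% to 53%.

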**The Motor Control Consequences of Excessive Physical Therapist Support in
Individuals with Stroke (NCT04856527)**

University of Cincinnati IRB Protocol 2020-1072

Most recent IRB approval: 2021-10-07

STUDY PROTOCOL AND STATISTICAL ANALYSIS PLAN

Study Protocol

Participants

Twenty participants aged 21-85 years¹ previously diagnosed with stroke (>1-month prior to enrollment to ensure medical neurologic stability) will participate in Experiment 1 (10 participants in experimental group, 10 participants in control group). Participants will be randomly assigned to a group. Participants must demonstrate independence or modified independence during ambulation (defined as the ability to ambulate with no physical assistance and use an assistive device as needed). Participants must score 0-3 on the Modified Rankin Scale (de Haan et al., 1995; Rankin, 1957), which indicates complete independence to moderate disability but able to walk without assistance. Participants must be able to maintain standing balance for >2 minutes with no physical support and maintain grasp of a handheld object with at least one hand. Participants are permitted to be active in programs of physical therapy or occupational therapy at the time of enrollment. All gender identities and all races/ethnicities will be eligible for participation.

Participants with stroke will be excluded due to limited language/cognitive abilities, deafness, blindness, or serious motor impairment that outright prevents performance of the experimental tasks (e.g., severe upper or lower extremity spasticity). Participants will be excluded if they are pregnant. Participants will also be excluded if they experience pain with weightbearing >4/10. Participants will complete the Mini Mental State Exam (Folstein et al., 1975) prior to study start to ensure cognitive capacity to engage in and consent to the study. Participants will be excluded if they have any other medical condition that would preclude the valid administration of the study measures, specifically seizure disorders, additional neurologic conditions beyond stroke, or significant musculoskeletal conditions (e.g., lower limb amputation).

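### The practice-period model tests group x trial against trial-to-trial scatter, so if trial is linear the test is too liberal when neighbouring trials are positively correlated or individual trajectories differ

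*Combined protocol and SAP*

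**What the plan says.** The Participants section sets the unit of randomisation and the size: "Participants will be randomly assigned to a group", with "10 participants in experimental group, 10 participants in control group". In the Practice section, "participants will engage in 10, 1 min practice blocks", and "Participants will rest for a self-selected period between each trial". The Design section gives the purpose: "To evaluate the role of therapist support during practice, each participant will complete 10 practice trials".

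The practice-period model is in the Statistical Analysis section, in a sentence that begins: "To assess performance (error score and postural sway metrics) during the practice period, trial number (1-10), group (experimental, control), and their interaction will be". It ends by saying that these terms are "entered as fixed effects and participant will be a random effect". That section then prescribes backward stepwise model building, with simple effects and pairwise comparisons after a significant interaction.

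Four things are not stated:
- whether trial number is numeric or a 10-level factor;
- whether the participant effect is an intercept only or also a slope over trials;
- any residual correlation between trials;
- the degrees-of-freedom method and alpha.

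**The concern.** Group is assigned to people. Whether the arms follow different courses over the ten trials should therefore be judged against how much individual courses differ between people. There are 20 such courses, which leaves 18 df.

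A random intercept removes differences in participants' level. It does not remove differences in trajectory, and it treats trials 1 and 2 as no more alike than trials 1 and 10. With linear trial, the interaction is then tested on about 178 df against within-person scatter. If neighbouring trials are positively correlated after the participant effect, or if people's true slopes differ, the standard error is too small.

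Eligibility makes identical true slopes a strong assumption: modified Rankin 0 to 3, ages 21 to 85, and any time beyond one month after stroke.

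At stake is a chance difference between 10 and 10 individual trajectories being reported as an effect of therapist support on performance during practice. A significant interaction also triggers follow-up comparisons. The model is run on error and every sway metric. Counting %DET, MAXLINE, MEANLINE, SampEn and SD in two planes, plus path length and error, that is 5 x 2 + 2 = 12 outcomes.

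**Working it through.** The plan states no power, alpha or effect size, so it has no figure of its own to reproduce.

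**Inputs from the documents.** 10 participants per group; 10 ordered trials each (200 observations); fixed effects trial, group and group x trial; participant as the only random effect.

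**Assumed inputs.** Two-sided alpha 0.05; normal errors with unit variance; residual lag-1 correlation r (AR(1)) after the participant effect; between-person SD of total change from trial 1 to trial 10.

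**Planned test, linear trial.**
- Participant slope: b_i = Σ(t − 5.5)·y_it / 82.5, where 82.5 = Σ(t − 5.5)² over t = 1 to 10.
- Test: t = (mean slope, experimental − mean slope, control) / √(s² × (2/10) / 82.5), with s² = RSS/178.
- Residual df: 200 − 20 participant means − 2 group slopes = 178.

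**Size of the error.** Let v be the true variance of one participant's slope, and W the expected sum of squares of one participant's ten values about their mean. Then E(s²) = (20W − 2 × 82.5 × v)/178. The variance ratio is R = v / (E(s²)/82.5), and the false-positive rate is about 2Φ(−1.96/√R).

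*Serial correlation, r = 0.5, identical slopes.* v = 0.02297 and W = 7.400. E(s²) = (147.99 − 3.79)/178 = 0.8101, so the model takes the slope variance as 0.8101/82.5 = 0.00982. R = 0.02297/0.00982 = 2.34, and 2Φ(−1.96/1.529) = 20.0%.

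*Differing slopes, r = 0.* A total-change SD of 1 residual SD is a slope SD of 1/9. v = 1/82.5 + 1/81 = 0.02447, and W = 9 + 82.5/81 = 10.019. E(s²) = (200.37 − 4.04)/178 = 1.103, so the model takes the slope variance as 0.01337. R = 1.83, and the rate is 14.7%.

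**Simulation under no group difference** (40,000 runs per setting; % rejecting at 0.05):

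| Setting | Linear trial, 178 df | Formula above | 10-level factor, F(9,162) | One slope per person, 18 df | Group contrast on participant means, 18 df |
|---|---|---|---|---|---|
| r = −0.2 | 2.2 | 2.1 | 5.6 | 5.1 | 5.2 |
| r = 0 | 5.0 | 5.0 | 5.0 | 5.0 | 5.2 |
| r = 0.1 | 7.1 | 7.1 | 5.2 | 5.0 | 5.1 |
| r = 0.3 | 12.8 | 12.6 | 6.2 | 5.0 | 4.9 |
| r = 0.5 | 20.0 | 20.0 | 7.7 | 4.9 | 4.9 |
| r = 0.7 | 28.8 | 28.7 | 9.9 | 5.2 | 5.0 |
| Total-change SD 1, r = 0 | 15.0 | 14.7 | 5.6 | 5.1 | 5.2 |
| Total-change SD 1, r = 0.5 | 27.2 | 27.3 | 8.7 | 4.9 | 4.9 |

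As a check on the shortcut, 400 REML fits of the random-intercept model per setting rejected 4.75% at r = 0 and 21.5% at r = 0.5.

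**The case against.** **Trial may be meant as a factor.** The plan lists trial number with its range in the same form as it lists the group levels, and it follows interactions with pairwise comparisons. That suits a 10-level factor at least as well as a slope. On that reading the excess is small (7.7% at r = 0.5). This stands, and the size must be given for both codings.

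**The size rests on assumed inputs.** Neither r nor the spread of slopes is in the documents. Self-selected rests could weaken carry-over, and negative serial correlation alone would make the linear test conservative (2.2% at r = −0.2). This also stands. The liberal direction is plausible but not established, so no single percentage should be quoted as the trial's error rate.

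**The practice model is not the test of learning.** A reader might infer that the plan's test of learning is inflated, or that group x trial is the only comparison of the arms on change. The documents support neither. The Design and Statistical Analysis sections assign learning to the model of pre-test against immediate post-test, where group x test condition also compares the arms on change. The practice model addresses performance, and during practice one arm is being physically supported.

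**The plan is under-specified, not wrong.** Naming participant as a random effect does not exclude a participant slope, and a slope would largely remove the problem. But the plan names none, and the ordinary fit of what is written has the narrow error bar shown above. The point is therefore more than a request for detail.

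**Conclusion.** The point holds for one term, group x trial in the practice-period model, on the random-intercept reading. With linear trial and an assumed two-sided 0.05, false positives run from about 7% to 28 to 29% for lag-1 correlations of 0.1 to 0.7. They are about 15% from differing slopes alone, at a total-change SD of one residual SD. With a 10-level factor they are about 5 to 10% over the same settings.

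Two wider conclusions do not follow. The whole practice analysis is not invalid: the group contrast averaged over the ten trials, tested on participant means, kept its level in every setting (4.9 to 5.2%). Correlation that comes only from differences in participants' level also does no harm, because the intercept absorbs it.

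Nor should a reader infer that the pre/post models are free of the issue. Trial order is specific to practice, but individual differences in change raise a similar question there, which is outside this point.

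The change should be made. It is not critical, because the plan's test of learning lies elsewhere.

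**What to change.** State in the practice-period paragraph that trial is coded as linear, and choose one of these tests for group x trial:

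1. Fit one least-squares slope over trials 1 to 10 per participant and compare the 10 v 10 slopes with a t-test on 18 df. With complete, normal data and equal slope variance in the two arms, this is exact whatever the serial correlation.
2. Keep the mixed model and add a participant-specific slope for trial, with AR(1) residuals if the fit converges, using Kenward-Roger or Satterthwaite df. Name option 1 as the fallback if the model does not converge or the slope variance is estimated as zero.

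State that the participant slope and the residual structure are exempt from backward selection.

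The cost is a sentence or two in the plan and a few lines of R, with no extra data or participants. The interval for this interaction will be wider, and its apparent power lower, on 18 instead of about 178 df. A linear slope will also miss a difference in course that is not roughly linear.

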All data processing and analyses will be completed using custom R scripts (v.4.0.3). All postural sway data (i.e., center of pressure—COP) will be filtered through a 4th-order lowpass zero-lag Butterworth filter with a cut-off frequency of 6 Hz prior to analysis.

Recurrence Quantification Analysis (RQA)

RQA (Webber & Zbilut, 2005) will be used to assess the regularity of postural sway. RQA quantifies the patterning, non-stationarity, and complexity of biological time series through the analysis of local recurrences in a reconstructed phase space (Riley et al., 1999a). Recurrence plots (RPs) provide a visualization of patterns of recurrence, where a single point on the RP indicates a recurrence and a line indicates continuing recurrence (Coco & Dale, 2014). A variety of metrics are used to quantify these patterns. Percent determinism (%DET) is the percentage of recurrent points which fall on diagonal lines

and reflects how often the system repeats the same sequence of points. Thus, higher %DET is indicative of a system with more regularity. Maximum line length (MAXLINE) is the length of the longest diagonal line segment on the RP, indicating the maximum duration of time that the system is revisiting an area of reconstructed phase space. Mean line length (MEANLINE) is the average length of diagonal line segments on the RP, indicating the average duration of time that the system is revisiting an area of phase space. In the context of the current study, reduced task-sensitive adjustments (i.e., modulation in task relevant direction) in %DET, MAXLINE, and MEANLINE of postural sway (hypothesized to exist following constraining posture/task) would indicate a more regular postural control system—one that is prone to repeating the same behaviors. RQA metrics will be calculated separately for each plane.

Sample Entropy (SampEn)

SampEn (Richman, Lake, & Moorman, 2004) will be used to evaluate changes in the predictability of postural sway as a convergent measure to complement RQA. SampEn evaluates the predictability of the next state of a system, given what is known about the current state of a system (Yentes, 2016). SampEn has been widely used to assess the regularity of postural control across a variety of task conditions and populations (e.g., Schmit et al., 2016). SampEn will be calculated separately for each plane.

Traditional Analyses

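### No learning contrast is fixed: backward selection and significance-gated follow-up together let p-values decide whether the group effect on laser and transfer learning is reported per hand, averaged over hands, or not at all

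*Combined protocol and SAP*

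**What the plan says.** The Design section gives the aim as a learning question: "To evaluate the learning effect in participants with stroke, the two groups (experimental, control), two hands (paretic, non-paretic), and two test conditions" form a 2 × 2 × 2 mixed design. Both hands are tested before and after practice: "Participants with stroke will complete 2 trials of each test condition per limb for a total of 8 test trials per participant". During practice only one hand is trained: "Participants with stroke will use the paretic hand".

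For the laser and transfer tasks, the Statistical Analysis section takes group, test condition and limb, "and their interactions will be entered as fixed effects, and participant will be entered as a random effect". The practice model has trial number, group and their interaction, with no limb factor. Two sentences then govern what is reported: "A backward stepwise approach will be used for model building" and "Simple effects and pairwise comparisons will be used to follow up on significant interactions".

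The document gives no removal criterion or significance level, exempts no term from removal and names no main contrast. It does not say whether full-model estimates will be reported whatever the selection result.

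**The concern.** The stated purpose of the test-phase models is "To characterize learning of the practiced supra-postural laser/target task and the associated postural sway patterns". The group difference in learning sits in two terms only, group × test and group × test × limb, and both can be removed. Three results are possible:

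- Three-way term kept: simple effects give a result for each hand.
- Three-way term removed, group × test kept: the result is an average of the practised and unpractised hands.
- Both removed: the final model contains no estimate of the group effect on learning.

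The first two answer different questions, and the third gives no answer. The p-values choose among them separately for each outcome. Yet the outcomes are meant to be read together; sample entropy, for example, is planned to corroborate the recurrence measures. That reading is difficult if one measure is reported per hand, another as an average, and a third with no group × test term.

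The factors are set by a randomised factorial design with no list of candidate covariates to thin out, so a model search has no clear purpose here.

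**Working it through.** **Counts from the documents.** Test trials per participant: 2 trials × 2 hands × 2 tests = 8, which agrees with the plan. Outcomes per model: 1 error score + 3 recurrence metrics × 2 planes ("RQA metrics will be calculated separately for each plane") + sample entropy × 2 planes + path length + SD × 2 planes = 1 + 6 + 2 + 1 + 2 = 12. Laser and transfer give 2 × 12 = 24 fits with the three-way choice. Practice adds 12 in which group × trial is only kept or dropped.

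**Assumptions.** The documents give group sizes (10 and 10) but no effect size, variance, correlation or removal rule. I assume:

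- post-minus-pre change per hand (mean of 2 trials) has variance 1;
- between-hand correlation of change ρ = 0.3, from participant-by-test variance ρ/2 = 0.15, with trial residual variance 1 − ρ = 0.7 (check: 2 × 0.15 + 2 × 0.7/2 = 1);
- a group effect of 1.0 in the paretic hand only, or in both hands;
- hierarchical removal at two-sided p ≥ 0.05.

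**Change scores** (20 − 2 = 18 df, critical t = 2.10).

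- Three-way term: variance of the between-hand difference 2(1 − 0.3) = 1.4; SE = √(1.4 × 2/10) = 0.529; 1.0/0.529 = 1.89; significant in 43%.
- Group × test: variance of the two-hand mean (1 + 0.3)/2 = 0.65; SE = √(0.65 × 2/10) = 0.361; 0.5/0.361 = 1.39; significant in 26%.
- With equal variances the two tests are independent. Per hand 43%; average 0.57 × 0.26 = 15%; neither 0.57 × 0.74 = 42%.
- Equal effect in both hands: the three-way term is kept in 5%; the average has ratio 1.0/0.361 = 2.77 and power 75%; split 5%, 0.95 × 0.75 = 71%, 24%.

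**Participant-intercept model as planned.** Within-participant residual df = 160 − 20 − 6 = 134. Of these, 18 df carry participant-by-test variation, with mean square 0.7 + 4 × 0.15 = 1.3; the other 116 have 0.7. Pooled: (18 × 1.3 + 116 × 0.7)/134 = 0.781. The model SEs are then √(0.4 × 0.781) = 0.559 for the three-way term (true 0.529) and √(0.1 × 0.781) = 0.279 for group × test (true 0.361). Simulation of the elimination (60,000 trials per scenario) gives the following, as per hand / average / no group × test term:

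| Scenario | Intercept model | Change scores |
|---|---|---|
| Paretic only, ρ = 0.3 | 42/25/32% | 43/15/42% |
| Paretic only, ρ = 0 | 35/22/43% | 32/22/46% |
| Paretic only, ρ = 0.5 | 50/25/25% | 56/10/34% |
| Both hands equally, ρ = 0.3 | 4/86/10% | 5/71/24% |
| Paretic only, ρ = 0.3, threshold 0.157 (AIC-like) | 65/21/13% | 67/16/18% |

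If participants also differ in their hand-to-hand gap (participant-by-limb variance 0.5 to 2 times the variance of change), the first intercept-model entry moves to 31/24/46% and 11/15/74%. With no true effect, some group × test term survives in 16% (intercept model) or 10% (change scores; 1 − 0.95² = 0.0975).

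**Which sentence is responsible.** I fitted the full intercept model with no elimination and applied only the gated follow-up. The split is 42.3/25.3/32.4%, against 42.3/25.1/32.6% with stepwise in the same run, and the two procedures give the same result in 99.6 to 99.8% of trials. In a balanced design the terms are orthogonal, so dropping one leaves the other estimates unchanged and only pools a few degrees of freedom.

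**Interval coverage, paretic contrast, intercept model.** Model SE √(0.2 × 0.781) = 0.395 against a true √0.2 = 0.447. The half-width is 1.978 × 0.395 = 0.781, or 0.781/0.447 = 1.75 true SEs: coverage about 92%. At ρ = 0.5 the pooled variance is (18 × 1.5 + 116 × 0.5)/134 = 0.634, the SE 0.356, and coverage about 88%. The 18-df change-score interval covers 95%.

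**The case against.** The strongest reply is that backward selection does little by itself here. That stands: the percentages measure significance-gated reporting, which the follow-up sentence would produce alone. A reader might infer that deleting the stepwise sentence cures the problem. It would not. What stepwise adds is that a non-significant group × test estimate can be missing from the final model.

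Other limits also stand:

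- A reader might infer that fixed contrasts would make the outcomes agree. They fix the quantity being estimated, not its significance. With 56% power for the paretic contrast, two independent outcomes with the same effect still differ in significance in 2 × 0.56 × 0.44 = 49% of trials.
- A reader might extend the per-hand or averaged ambiguity to all 36 fits. The practice model has no limb factor, so it covers 24.
- Eleven of the 12 outcomes are whole-body sway measures, for which a limb average is reasonable. If both hands respond equally, the average is the usual result. The plan also expects sway effects to differ by plane, so identical effects across outcomes are not its premise.
- Exaggeration of significant estimates is not special to selection: a fixed paretic contrast with true value 1.0 averages 1.30 when significant.
- The coverage shortfall comes from the random-effects structure, not from selection. It matters here because the fix relies on confidence intervals.

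The authors may intend to tabulate full-model estimates anyway, but the document does not say so.

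**Conclusion.** The concern holds for the two sentences taken together. As written, the plan fixes no learning contrast, and significance decides what is reported for each of 24 laser and transfer fits. That follows from the text without simulation.

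The size is illustrative. For a 1.0 SD paretic-only effect the split is about 42/25/32% (intercept model) or 43/15/42% (change scores); for an equal effect in both hands it is 4/86/10% or 5/71/24%. These figures depend on the assumed effect, correlation, variance structure and threshold, and the table shows that they move materially with each. The documents do not support blaming stepwise selection alone, or promising more power or agreement between outcomes from a fixed model. The gain is that every outcome reports the same pre-stated quantities, estimated without selection. This should be fixed before analysis.

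**What to change.** - Delete the stepwise sentence and remove the significance condition on follow-up for the learning contrasts.
- Keep the full group × test × limb models (laser, transfer) and the group × trial model (practice) whatever the p-values.
- For every laser and transfer outcome, report with 95% CI the group × test estimate for each hand, the limb average and the three-way term. For practice, report the group × trial estimate with its CI.
- Name one main contrast in advance. The paretic hand is natural for laser error because it is the practised hand. For sway, paretic hand or limb average is the sponsor's choice.
- For laser and transfer, take CIs from participant-level post-minus-pre change (18 df), or add participant-by-test and participant-by-limb random effects.

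Cost: a few sentences in the analysis section and no extra data. Non-significant terms stay in the tables. If both hands benefit equally, the paretic contrast has less power than the average (56% v 75% with change scores in the illustration). Reporting four contrasts gives at least one p < 0.05 in about 14% of null outcomes, against 5% for a single contrast, which is why one must be named as main.
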